two groups. The data for all time points will then be fitted to a multivariate model under a negative binomial distribution using DESeq2 with diet group, time point, interaction between diet and time point, baseline BMI, age, sex, and smoking status as covariates. This model will be compared to a reduced model that does not include the diet:time point interaction⁽⁷⁰⁾. A likelihood ratio test will be used to identify microbes with differential abundance by diet at time points after baseline. Estimates of significance will be adjusted for multiple hypothesis testing⁽⁷¹⁾. OTUs that are differentially abundant on a HPD will be grouped by hierarchical clustering, which we anticipate will highlight distinct kinetic patterns of microbial change.

Expected results/potential pitfalls: We do not anticipate problems with the collection or transportation of fecal samples to our clinical research unit. We predict that *Akkermansia* will significantly increase on a HPD as was seen in our rodent studies. We further predict that most HPD-responsive microbes will have altered abundance within the first 3 to 7 days as has been observed in other dietary studies^(72,73). We estimate a 20% dropout rate based on our high protein meal replacement study, leaving approximately 80 subjects per group. This compares favorably to published studies reporting dietary effects on the microbiome using sample sizes of 10-15^(72,73,74). We anticipate that a HPD will have a similar magnitude of effect as these previously studied diets and hence we expect to have sufficient numbers to detect compositional differences.

2.2 Identification of metagenes affected by a high protein diet.

Experimental protocol: We will assess the functional consequences of altered microbial composition by sequencing the genes carried by intestinal microbes. Shotgun sequencing of DNA extracted from fecal samples will be performed using the HiSeq 3000 with a target depth of 10 GB data per sample, comparable to the 11.7 GB depth used by the Human Microbiome Project for stool samples⁽⁷⁵⁾. Due to the costs of sequencing at this depth, we will only sequence baseline samples and samples from day 112.

Shotgun reads will be inputted into HUMAnN2 for annotation of gene families and identification of the microbial source of these genes⁽⁷⁶⁾. Individual genes will be aggregated into functional pathways using the MetaCyc database⁽⁷⁷⁾. Gene and pathway abundance for the HPD and NPD groups at baseline will be compared to confirm that randomization prevented skewing of the functional profiles of the two groups. Pathway abundance will be fitted to a multivariate model using DESeq2 with diet group/time point, baseline BMI, age, sex, and smoking status as covariates to identify functional pathways impacted by a high protein diet after adjusting for covariates. Genes belonging to HPD-associated pathways, stratified by the genus of their microbial source, will then be individually evaluated using DESeq2. This approach will reduce the number of statistical tests which might be overwhelming given the greater than 5 million genes within the intestinal metagenome⁽⁷⁵⁾. HPD-associated genes will be visualized in pathway maps to highlight the specific metabolic shifts in the microbiome at the DNA level that occur on a HPD.

Expected results/potential pitfalls: We predict that a HPD will reduce the abundance of genes in phosphotransferase pathways involved in bacterial carbohydrate metabolism, which are elevated in obese humans⁽²⁴⁾. Our estimated final sample size of 80 subjects per group would be much larger than existing metagenomics studies of obese patients which have used 6-7 subjects per group at lower sequence depths (3 GB per sample in the most recent study)^(24,26). We anticipate that the magnitude of effect of a high protein diet will be less than that in those comparisons (obese vs. lean, gastric surgery vs. non-surgically managed) but that the 10 fold larger sample size will provide sufficient power to detect metagenomic shifts.

C. Aim 3. Identify fecal microbial predictors of response to a high protein diet.

Rationale and hypothesis: The second aim of this proposal focuses on the relationship of the microbiome to clinical endpoints including weight loss, body fat loss, lipids, and

hyperglycemia. We hypothesize that subjects will vary in the responsiveness of their microbiota to a HPD based on baseline or post-dietary intervention levels of microbes such as *Akkermansia muciniphila* that respond to the HPD. The impact of these microbial changes on diet-induced weight gain will be assessed in humanized gnotobiotic mice.

Study design: This is a randomized study using the same subjects described in Aim 1. Nutritional assessment, physical examination, bioelectrical impedance, laboratories will be performed at baseline, and weeks 2, 4, 6, 8, 12 and 16. Stool samples will be collected on day 3, 7, 14, 17, 21, 28, 42, 56, 84 and 112.

Study timeline: Data collection will be completed at week 16. The stool samples collected during the study period will be used for 16S rRNA sequencing, shotgun metagenomics, and data analysis.

Bioinformatics protocol: Patient characteristics (physical measurements, lean body mass, laboratories, demographic traits) at baseline will be compared using a 2-sided t-test (for numerical variables) or chi-square test (for categorical variables) to evaluate the randomization. 3DFR and FFQ performed at each timepoint will be used to assess the predicted protein content of the patient's diet compared to baseline to evaluate the success of the dietary intervention. Clinical response endpoints significantly associated with HPD in Aim 1 will then be correlated with the abundance of microbes found to be enriched or depleted on a HPD in Aim 2.1. These endpoints will be fitted to multivariate models to adjust for baseline clinical covariates including BMI, age, sex, and smoking status. Spearman correlations will then be calculated for all combinations of residuals for the clinical endpoints and for microbial abundance (using DESeq2 fitted multivariate models from Aim 2.1 to adjust for covariates). Separate correlation analyses will be performed at baseline and each of the time points during treatment.

Microbes that are independently associated with clinical response to a HPD will then be used to create random forests classifiers to predict response. Subjects in the HPD group will be identified as responders if they had a decrease in any of the clinical endpoints that exceeded the predictions of the multivariate model for the NPD group. The sensitivity and specificity of the classifiers will be estimated using 10-fold cross-validation. Classifiers constructed from baseline microbial abundance and microbial data at each time point will be compared to determine the earliest time point when accurate predictions of response are possible.

The above analytic pipeline will then be applied to the shotgun metagenomics data obtained at baseline and day 112. Gene families and/or metabolic pathways that shift in response to a HPD may be more consistent across diverse populations than abundance of specific microbes such as *Akkermansia* which could vary greatly from person to person⁽⁷⁸⁾. The performance of classifiers constructed from metagenes will be compared to those built from microbial abundance to identify the approach that is most predictive for response.

Expected results/potential pitfalls: We predict that a subset of the HPD-associated microbes and metagenes will be associated with response in the HPD. We also expect that baseline and/or post-dietary intervention abundances of microbial features can be used to generate accurate random forests predictors for clinical response. We used similar bioinformatics approaches to identify the inverse correlation of *Akkermansia muciniphila* with body fat in our rodent model and to predict IBD status in families with pediatric inflammatory bowel disease. Accordingly, we do not anticipate problems performing these analyses.

Human Subjects

1. Risk to Subjects

(a) Human Subjects Involvement and Characteristics:

Approximately 198 healthy volunteers age 30 years and older between BMI of 27 to 40 kg/m² will be able to take part in this study. Pregnant women or women likely to become pregnant during the course of the study may not participate in this study. Female subjects must not be

able to conceive by reason of surgery, radiation, 1 year past the onset of menopause, or an approved method of contraception. No vulnerable subjects will be included in the study. (See the detail in the Research Plan, Proposed Work, Aim 1, Sections of Recruitment, Procedures, and Statistical Analysis)

(b) **Sources of Materials:** See the detail in the Research Plan, Proposed Work, Aim 1, Section of Procedures.

(c) **Potential Risks:**

Blood Draw: There are other possible risks or discomforts that may be experienced during this study. Subjects may experience pain, bruising, and/or burning at the site where blood is taken. Blood clot formation, infections, or bleeding may also occur, but these are rare. Subjects may also experience fainting during or shortly after having blood drawn. If subject experiences fainting symptoms, such as dizziness or light-headedness, he/she should lie down immediately to avoid possible injury caused by falling and should notify study personnel immediately.

Women of Child-Bearing Potential: There might be unknown risks to the unborn child if the subject is or becomes pregnant during the study. Due to these risks, subjects must not participate in this study if they are pregnant, or plan to become pregnant during the research study period, or are breast-feeding a child. If the subject is a woman of child-bearing potential: by signing the consent form, they confirm to the best of their knowledge that she is not pregnant now and does not intend to become pregnant during this study. A pregnancy test will be done to confirm that she is not pregnant before she takes part in this study and she must avoid becoming pregnant during the study by using an acceptable form of birth control as described below. If at any time during this study the subject thinks she might be pregnant, or later learn that she was pregnant during the study, she must contact the study doctor immediately for further instructions about her participation in this study and follow-up. The following forms of birth control are considered acceptable: intrauterine device, implantable progestin device, progestin intramuscular injection, oral, transdermal, or vaginal contraceptive (started at least 1 month before Visit 1 and continuing for entire study) condoms with spermicide, Single-barrier methods alone (such as condoms without the use of spermicide) and rhythm methods are not acceptable methods of birth control. Since subjects will not be receiving the study drug for the treatment of a health problem, alternative treatment does not take part in this research study.

Bioelectrical Impedance Analysis (BIA): This noninvasive tool is a commonly used to measure body fat. The impedance measurement is considered safe because of several factors. One factor is that currents at a low frequency are reported to be unlikely to stimulate nerves or cardiac muscle. There have been no reports of adverse events caused by BIA, even in the course of thousands of individuals undergoing measurement. Relatively small current magnitudes are involved, which are less than the threshold of perception. Furthermore, the use of batteries or low-voltage power sources greatly diminishes risks from a shock. Patients with implanted cardiac defibrillator will be excluded from the study to prevent potentially incorrect defibrillator responses.

Hepatic Transient Elastography: Sound waves are used to determine the density of tissues based on the amount of water content in the body. Transient Elastography is thus noninvasive and does not use any radiation. Patients may experience slight discomfort related to positioning the ultrasound probe along the abdomen. They will be advised to minimize discomfort through positioning themselves and visiting the exam room in advance or using relaxation techniques.

Fecal collection: Collection involves passing a bowel movement into the provided toilet hat and using a plastic spoon to store a sample in an insulated container. Other than discomfort in collecting stool samples, there is minimal risk to potential subjects.

2. Adequacy of Protection from Risks

(a) Recruitment and Informed Consent: All subjects who are considered for this protocol will be evaluated by the PI or co-PI. Following the explanation of the protocol and the consent form, the subjects will be asked about their level of comprehension of the study. Subjects may be asked to restate study purpose and their role in participation to verify understanding. Only when the study doctor is assured that the prospective subject understands all aspects of the study and is consenting to participate freely and without coercion, will the study doctor have the prospective subject sign the informed consent form. Potential subjects that are not able to understand the protocol will not be considered to be eligible for entry into the clinical study.

(b) Protection against Risk: All procedures will be fully explained to the subjects prior to the start of the screening. All questions will be answered as needed for the subject reassurance. All procedures will be conducted by trained and qualified medical personnel. Subjects will be asked to report all side effects and adverse experiences. Blood drawing supplies are sterile and single use only. The staff is trained and certified in Phlebotomy (blood withdrawal). If there is any evidence of an allergic reaction or adverse effect from the protein meal, the subject will be monitored, and all reactions will be followed up with the PI until resolution. The subject may be discontinued from the study if deemed necessary by the study doctor. Subjects will be provided with a telephone number to contact the study staff in the event of emergency or adverse events.

3. Potential Benefit of the Proposed Research to the Subject and Others.

Subjects will not experience any direct health benefits during or after completing this study. A potential medical benefit subjects may derive from participating in this study is the detection of an unsuspected medical condition from tests performed (for example, physical exam and blood tests). In addition, the information about the study may benefit others in the future. The information learned from this study will enable doctors and scientists to understand the regulation of GI hormones in obesity.

4. Importance of the Knowledge to be Gained.

Metabolic syndrome is a common problem in the VA and, thus, the overall direction of this project is well suited for the VA. Strategies to help veteran patients lose weight would definitely decrease morbidity and mortality and would be cost saving for chronic care of complications from obesity.

ADVERSE EXPERIENCES

Patients will be monitored and questioned regarding the occurrence and nature of any adverse experiences. An adverse event is any change in the physiological or psychological state, other than the primary condition, that qualifies the patient for this study. Adverse events are first graded according to seriousness and then severity. Additionally, the Investigator must decide if the occurrence of the adverse event is related to the study product. A description of the event and its relationship to study product must be reported on the adverse events case report form for each adverse event recorded in the patient's chart.

Definition of serious adverse event

A serious adverse event, as defined in Title 21 of the code of federal regulations, Part 312, subpart ID, Section 312.32, means any adverse experience occurring at any dose that results in any of the following outcomes: death, a life-threatening adverse drug experience, inpatient hospitalization or prolongation of existing hospitalization, a persistent or significant disability/incapacity, or a congenital anomaly/birth defect. Important medical events that may not result in death, be life-threatening, or require in-patient hospitalization may be considered a serious adverse experience when, based on appropriate medical judgment, they may jeopardize the patient or subject and may require medical or surgical intervention to prevent one of the outcomes listed in this definition. An adverse event is usually considered by the Sponsor to be

serious if severity for the event is graded as 3 (severe) or 4 (immediately life-threatening or fatal).

Data Safety Monitoring Procedure

Any adverse event (AE) will be recorded as described below. All AEs will be reviewed by the investigator and co-PI for the proposal. If it is deemed to be a serious AE these will be recorded and submitted to the IRB for review.

Severity

For evaluation and reporting purposes, the clinical severity of the event is stratified into four classes. The four classes of Severity are 1-Mild, 2-Moderate, 3-Severe, or 4-Immediately Life-Threatening/Fatal.

Life-Threatening Adverse Experience

A life-threatening adverse experience is defined as any adverse experience that places the subject, in the view of the investigator, at immediate risk of death from, the reaction as it occurred, i.e., it does not include a reaction that, had it occurred in a more severe form, might have caused death.

Association with the use of Study Product

Association with the use of the study product means that there is a reasonable possibility that the adverse event may have been caused by the product under investigation. All adverse events are graded with regard to their association with the use of the study product. The classifications used include Not Related, Unlikely Related, Probably Related and Definitely Related.

Unexpected Adverse Event

An unexpected adverse event is any adverse product experience that is not consistent with the current nutritional product insert in specificity or severity.

Adverse Event Reporting Procedure

The Investigator must report to the occurrence of any *serious* adverse events, regardless of relationship to study product, or the first occurrence of any unexpected or previously unknown clinical event (regardless of Grade). A written report (Report for Serious/Life Threatening Events) of the event must be faxed within 5 working days to The VA GLAHS Institutional Review Board (IRB).

PREMATURE WITHDRAWAL OF PATIENTS

Whenever possible, patients will be studied for a minimum of 2 weeks. The patient's participation in the protocol will terminate under any of the following circumstances:

- At any time for any reason.
- Physician determination that patient's further participation in the protocol is not in the patient's best interest.
- At the determination of the sponsor.
- For any discontinuation, the investigator will obtain all the required details and document the date of and the reason for the discontinuation. If the reason for removing a patient is an AE, the specific event or the main laboratory abnormality will be recorded in the source.

**THE INVESTIGATOR WILL MAKE THOROUGH EFFORTS TO DOCUMENT THE OUTCOME
GOOD CLINICAL PRACTICES/ETHICAL CONSIDERATIONS**

This study will be conducted in accordance with Good Clinical Practices, Title 21 of the Code of Federal Regulations, Part 50, Subparts A and B; Part 56; and Part 312, Subpart D, and the 1996 International Conference of Harmonization (ICH) *Guideline on Good Clinical Practices*.

Data Collection

Source documents will be utilized for each patient entered into the study. Study participants will NOT be identified by name on any study documents. Patients will be identified by a patient identification number (PIN). Investigators will keep a patient code list accessible. All data collected will be stored in a secure locked file cabinet in accordance with the VA's Data Safety policies.

ETHICAL CONSIDERATIONS

The investigator will ensure that the study is conducted in full conformance with the FDA standards for human research as specified in 21 CFR 312.

Institutional Review Board (IRB)

The VA GLANS operates a Department of Health and Human Services-approved Institutional Review Board with a Federal Wide Assurance (FWA) agreement in place since the 2003 (FWAA00004642).

Institutional Review Board Approval

An Institutional Review Board (IRB), which is duly registered with the FDA and operating in accordance with Title 21 of the Code of Federal Regulations Part 56, must approve the Clinical Protocol and corresponding Informed Consent Document and agree to monitor the conduct of the study and periodically review its progress at regular intervals.

Informed Consent

All study participants must sign an informed consent. The investigators will inform all subjects as to the nature, aims, duration, potential hazards, and procedures to be performed during the study and that his or her medical records, may be reviewed by the FDA. This protocol must receive approval by the Institutional Review Board prior to implementation. The investigator must also explain that the patients are completely free to refuse to enter the study or to withdraw from it at any time. The protocol will be discussed in detail with all potentially eligible patients. All revisions of the protocol must be reflected in the consent form and reviewed by the IRB.

Patient Confidentiality

All reports and patient samples will be identified only by a coded number to maintain patient confidentiality. All records will be kept confidential to the extent permitted by law. The investigator should keep a separate log of patients, codes, names, and addresses. Documents which identify the patient by name (informed consent) should be kept in strict confidence.

Patient's Financial Responsibilities during the Study

Patients will not be financially responsible for any procedures or tests of any investigational nature.

GENDER AND MINORITY INCLUSION

In accordance with Part VIII of the Federal Register, NIH Guidelines on the Inclusion of Women and Minorities as Subjects in Clinical Research (NIH, March 1994), women and members of minority groups and their subpopulations will be included in this research.

Multiple PD/PI Leadership Plan

[name], and [name], PhD, are co-PIs for the proposed project. [name] has expertise in molecular/cellular biology studies and human clinical studies and thus will have the principal responsibility for directing the human clinical studies and molecular biological studies. He will oversee the experimental design assessment of methodological approaches, review the data, plan new projects, follow the advancement of the field in the areas of the project and be responsible for publications of the results derived from the work.

[name] has had extensive experience planning and implementing microbiome studies in patient cohorts and in animal models, including a rat model of Western diet-induced obesity that responds to a high protein diet. He will oversee the processing and sequencing of stool samples and the bioinformatics analysis of the microbiome sequence data. The co-PIs will have monthly laboratory meetings to review and interpret data from the proposed studies with a focus on translating the results obtained from basic science projects to the design of human trials as well as to translate data obtained from the proposed human clinical data to confirmatory testing in the animal models core. The co-PIs have worked together on projects for several years and thus have developed collaborative projects previously. Any budgetary issues will be resolved by the ACOS Research and Development, [name]. It is unlikely that there will be differences in how the budget will be executed since the co-PIs have had a close working relationship and given that the purpose of this proposal is to develop new and innovative research directions focused ultimately on improving the healthcare of veterans with obesity disorders.

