i. Study Design: This randomized controlled study will assign approximately 200 subjects (100 each) to the following arms (Appendix 1): 1) High protein diet group based on 1 gram of protein per pound of lean body mass, and 2) Standard protein diet group as control based on 0.5 gram protein per pound of lean body mass with same calories. All participants will meet with a registered dietitian, physician or nurse practitioner to assist them with their diet efforts in all the arms. In the study, the percent energy from fat will be held constant at 30% and the differences in the diets relate only to the protein and carbohydrate contents (30% protein and 40% carbohydrate, and 15% protein and 55% carbohydrate respectively). At the initial visit patient will not be calorie restricted but will have standardization of their nutritional macronutrient intake based on their group randomization. At the 2 week visit patient will then begin a 1500 calorie restricted diet with the same macronutrient composition (ie. 30% protein and 40% carbohydrate, and 15% protein and 55% carbohydrate respectively for the high and standard protein groups).

ii. Number of Subjects: Approximately 200 healthy volunteers age 30 years and older with a BMI between 27 to 40 kg/m² will be able to take part in this study.

iii. Estimated Study Duration: Accrual period is 3-4 years; anticipated dropout rate is 20%; and total study duration is approximately 5 years (taking into account data analysis).

iv. Subject Eligibility: Subjects will be assigned an enrollment number after signing the informed consent form. The subjects will complete all the screening tests and procedures as listed. When a subject completes the screening tests and procedures, the subjects will be assigned a randomization number. Subjects will be randomized into one of the two diet groups as described in Appendix 1.

The practitioner at screening will obtain each subject's date of birth, sex, race, medical history, current medications, and smoking and alcohol history. The physician will perform complete physical examinations. Height will be measured using a standardized stadiometer, while the subject stands

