Stool samples will be collected on day 3, 7, 14, 17, 21, 28, 42, 56, 84 and 112. Subjects will be provided with kits for home sampling. The subjects will urinate first then defecate into the Fisherbrand Commode Specimen Collection System. Subjects will use a spoon to transfer freshly defecated feces to a Para-Pak stool collection cup prefilled with 95% ethanol to fix the samples, allowing storage at room temperature for up to 2 weeks. The remaining feces will be frozen. This involves removing the cup from the toilet hat, tightly closing the lid, and transferring the cup to a Ziploc bag for storage in the subject's freezer. Frozen samples will be delivered to the VA clinic during scheduled study visits using a Styrofoam box and frozen packs. Subjects who forget to bring samples will be provided with prepaid envelopes to mail their samples to the coordinator. Samples will be stored at -80°C. Ethanol-fixed and fresh frozen samples give comparable metagenomics results to samples stored in preservatives such as RNALater while minimizing subjects' risk of exposure to toxic chemicals ⁽³³⁾.

Statistical Analysis:

Statistical Design: This is a 2-group randomized nutritional study to evaluate whether the high-protein diet will improve weight loss in comparison to a standard (control) diet. Eligible subjects will be randomly assigned into one of the two groups in a ratio of 1:1.

Sample Size Determination: The sample size is determined based on the Specific Aim 1 to significantly improve weight loss, as observed by comparing the high-protein diet to the standard diet. The primary outcome of interest is weight loss at 16 weeks (the end of the study). An evaluable sample size of at least 165 (i.e., 55 per arm) will achieve 80% power to detect an effect size of 0.245 using an F test with a two-sided 0.05 significance level when comparing each of the two high-protein diets to the standard diet, assuming that the mean weight loss for the standard diet is 14 lbs with the common standard deviation within group of 10 (from preliminary data), and the size of the variation in the means is 2.45. To account for an attrition rate of up to 20%, we will enroll a total of 200 subjects (66 per arm). Preliminary data suggest that the estimated effect size ranges from 0.23-0.34 when comparing the high-protein diet to the standard diet.

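### The stated 80% power belongs to a three-arm F test; the two-arm trial has no stated power or target difference in pounds

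*Combined protocol and SAP*

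**What the plan says.** The design is two-arm throughout the operative text. Under Statistical Design (4. Work Proposed, Aim 1, Statistical Analysis): "This is a 2-group randomized nutritional study", allocated 1:1. Under Procedures, Study Design: "This randomized controlled study will assign approximately 200 subjects (100 each) to the following arms", one high protein and one standard protein. Section 2.1 under Aim 2 expects 20% dropout, "leaving approximately 80 subjects per group".

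Sample Size Determination, directly after the two-group statement, describes something else: "An evaluable sample size of at least 165 (i.e., 55 per arm) will achieve 80% power to detect an effect size of 0.245", by an F test at the 0.05 level, "when comparing each of the two high-protein diets to the standard diet". Its inputs are a mean loss of 14 lb on the standard diet, a "common standard deviation within group of 10 (from preliminary data"), and "the size of the variation in the means is 2.45". Enrolment is then set: "we will enroll a total of 200 subjects (66 per arm"), to cover attrition of up to 20%. The paragraph closes with an effect size range of 0.23–0.34 from preliminary data, without naming the study or the effect-size metric.

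The Data Analysis, Primary Endpoint and Secondary Statistical Analyses paragraphs still mention three diet groups in places. However, the primary objective is stated as high-protein against standard, and the first secondary model codes diet with two levels.

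**The concern.** The power statement for the primary endpoint should describe the comparison that will be made. Here it assumes three arms, a per-arm size that is neither the randomised nor the expected evaluable number, and a second high-protein diet that appears nowhere else in the protocol. No expected high-protein mean and no between-arm difference in lb is given, and no power is given for 80 or 100 per arm.

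Without a difference fixed in advance, a null result at 16 weeks cannot be judged against what the trial was meant to detect. Nor can a reader tell from the plan whether 200 subjects is too few, about right or generous.

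**Working it through.** **Inputs** (Sample Size Determination unless noted): within-group SD 10, SD of the group means 2.45, two-sided alpha 0.05, 55 per arm; 100 randomised per arm (Study Design); about 80 evaluable per arm (Aim 2, section 2.1).

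**Method.** One-way F test with k groups of n: f = SD of means / within-group SD; noncentrality λ = N f²; degrees of freedom k − 1 and N − k. Power is from the noncentral F distribution.

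**1. Reproduce the plan's figure.** f = 2.45/10 = 0.245. With k = 3 and n = 55, N = 165, λ = 165 × 0.245² = 9.90, df 2 and 162: power 80.4%. At 54 per arm it is 79.6%, so 55 is the smallest n that reaches 80%. The enrolment figure has the same origin: 3 × 66 = 198, whereas 2 × 66 = 132.

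**2. Same f, two arms.**

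- n = 55: N = 110, λ = 6.60, power 72.1%.
- n = 67: power 80.4%, the smallest n that reaches 80%.
- n = 80: N = 160, λ = 9.60, df 1 and 158, power 86.9%.

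**3. What difference in lb is meant?** Several patterns of means have an SD of 2.45. For a two-arm comparison with SD 10, f = difference/20.

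| Pattern | Difference | Two-arm f | Power at 80 per arm |
|---|---|---|---|
| Two means | 2 × 2.45 = 4.9 lb | 0.245 | 86.9% |
| Three means, both high-protein arms equal | 2.45 × 3/√2 = 5.2 lb | 0.26 | 90.4% |
| Three equally spaced means, one step | 2.45 × √1.5 = 3.0 lb | 0.15 | 47% |
| Three equally spaced means, full range | 2 × 3.0 = 6.0 lb | 0.30 | 96.5% |

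The equally spaced pattern could be 14, 17 and 20 lb (SD 2.449). That is an inference; the plan does not state it.

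**4. Detectable difference.** At 80 per arm, 80% power corresponds to 0.446 × SD, which is 4.5 lb at SD 10.

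**5. The 0.23–0.34 range.** If it is Cohen's f, two arms with SD 10 give 20 × 0.23 = 4.6 lb to 20 × 0.34 = 6.8 lb, and 82% to 99% power at 80 per arm.

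**6. Sensitivity to the SD.** Section 3.1.B compares the same two protein levels over 3 months: −11.1 against −11.9 lb, p = 0.80, 42 and 44 subjects. Assuming an unadjusted t test, t = 0.254 on 84 df, so SE = 0.8/0.254 = 3.15 lb and SD = 3.15/√(1/42 + 1/44) = 14.6 lb. Rounding of the difference and p-value allows about 12 to 17 lb. At SD 14.6, 4.9 lb has about 56% power at 80 per arm.

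Section 3.1.A points the other way. Reading ± as SE and assuming the 77 completers split 38/39, the SDs are 0.81 × √38 = 5.0 and 0.72 × √39 = 4.5 percentage points, about 4.75 pooled. The difference is 4.57 − 2.25 = 2.32 points, so f = 2.32/(2 × 4.75) = 0.244. At an assumed body weight of 210 lb, 4.75% is about 10 lb.

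**The case against.** The strongest reply is that the slip is harmless. At the plan's own f and SD, two arms need 67 evaluable subjects each and about 80 are expected, so correcting the design raises power from 80% to 87%. The apparent attrition shortfall (200 × 0.8 = 160, below 165) also disappears, because 165 is a three-arm target. The leftover references to three groups do not change the test that would be run. All of this stands, and it limits the finding to a misstatement. It does not supply the missing target difference, and it relies on carrying f across designs, which the plan never says it does.

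A second reply is that SD 10 is reasonable. Section 3.1.A is compatible with both f = 0.245 and an SD near 10 lb under the assumptions above, although a 52/52 split would give f = 0.21 and about 11.6 lb. The 14.6 lb figure is fragile: it comes from rounded 12-week values and an unspecified test, in a section whose counts disagree (60% completion against 86 of 100 subjects; 46 against 44 in the standard arm). Any gain from the ANCOVA is also uncounted. This is fair. The SD point supports naming the source and adding one sensitivity note, not a second set of power figures.

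A reader might go further and take 0.245 as a standardised mean difference, that is 2.45 lb, and conclude that power is only about a third. The text excludes this. It ties 0.245 to the variation in the means over the within-group SD, which is Cohen's f, and as a standardised difference 55 per arm would give about 25% power, not 80%.

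**Conclusion.** The sample size paragraph is wrong as written. Its 80% is the power of a three-group omnibus F test at f = 0.245, not of the two-arm trial, for which the plan states neither power nor a target difference in lb. Carried over to two arms with SD 10, the plan's f corresponds to 4.9 lb and about 87% power at 80 evaluable per arm. The three-arm origin leaves 3.0, 5.2 and 6.0 lb open as well, with 47%, 90% and 96.5% power.

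A reader might infer that the trial is underpowered, or that the section 3.1.B result rules out the assumed benefit. The documents support neither. Underpowering would need a target well below 4.9 lb or an SD well above 10, and the plan establishes neither. The section 3.1.B result has a 95% interval from 7.1 lb favouring standard protein to 5.5 lb favouring high protein, so it does not exclude 4.9 lb.

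These figures assume 20% loss from 100 per arm, an unadjusted comparison of mean change, and SD 10 unless stated.

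**What to change.** Replace the calculation, at the existing N, with:

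> With 100 subjects randomised per arm and up to 20% attrition, about 80 evaluable per arm give 87% power (two-sided alpha 0.05) to detect a 4.9 lb difference in mean 16-week weight loss between the high-protein and standard diets, assuming SD 10 lb; the difference detectable with 80% power is 0.446 × SD (4.5 lb at SD 10).

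The sponsor should then:

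- confirm 4.9 lb as the target, or state another difference with its justification and power;
- name the preliminary study behind SD 10 and behind the 0.23–0.34 range, and say that the range is Cohen's f if it is;
- add one sensitivity sentence: section 3.1.B suggests an SD nearer 14.6 lb (about 12 to 17), at which 4.9 lb has about 56% power, while section 3.1.A is compatible with about 10 lb under stated assumptions;
- delete 165, 55 per arm, 66 per arm and the mention of two high-protein diets, and change three to two in the Data Analysis, Primary Endpoint and Secondary Statistical Analyses paragraphs.

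This is wording only, with no extra subjects and no change to conduct. The cost is that the stated detectable difference may become less favourable if the sourced SD exceeds 10.
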